#### Abstract

**Background:** There is a need for stronger community involvement with the elderly, specifically those with feelings of loneliness. Large proportions of elders in previous studies reported feelings of loneliness, and loneliness at advanced ages is a growing trend seen within the last thirty years despite advances in technology and social media. We propose a randomized control trial to determine the effectiveness of a volunteer-based lunch program on decreasing feelings of loneliness in elderly participants. *Methods:* Lonely elders in the community will be identified and matched with a trained medical student. Each student will bring provided lunches once a week to their elder participant's residence, and they will share lunch together for an hour once a week for six weeks. Enrollees are eligible for the study if they are over 60 years of age, speak English, have feelings of loneliness on the three-item scale, and display no cognitive impairment. The participants will be assessed pre and post intervention using the R-UCLA scale for loneliness, PHQ-9 for depressive symptoms, and GAD-7 for feelings of anxiety. Participant satisfaction will be assessed using Likert items as well as open-ended questions. Intervention group responses will be compared to responses of participants that did not receive the lunch meeting intervention. *Discussion:* Success of such a companion lunch program would provide an effective route to combat loneliness in the elderly.

**Keywords:** *Loneliness, elderly, depression, anxiety, RCT.* 

## 1.0 Background

Since the 1960's, the elderly population in the United States has grown steadily. By 2030, one in three people in the U.S. will be over the age of 65 [1]. In addition to being at a greater risk for chronic disease, the elderly are also more vulnerable to being socially isolated and lonely. Simply living alone does not appear to be a significant predictor of loneliness, as the elderly could still have a strong support network while living alone, but prevalence data suggests that one in three adults over the age of 65 are lonely [2]. Furthermore, the oldest of the elderly seem to be the loneliest. Dykstra et al. in a 2009 study estimate 40 to 50 percent of those aged 80 or older to be lonely [3].

Loneliness has been previously defined as the difference between desired and actual relationships, and there is a distinction between loneliness and social isolation [2]. While being considered socially isolated is due to lack of social contact, loneliness is assessed by perceptions of social isolation. Feelings of disconnect, isolation, and not belonging are much more indicative of loneliness than simple aloneness and lack of social contact [4]. Not having a support network or anyone to confide in can lead to feelings of social isolation, and despite advances in technology and the development of social media, feelings of loneliness have increased in the past thirty years [5]. The proportion of Americans who said they had no one to talk to about important matters increased from 10% in 1985 to 25% in 2004 [6]. This is an alarming trend because social support has been consistently shown to increase the likelihood of survival. In a meta-analytic review from 2009, participants with strong social relationships and support were found to have a 50 percent increased likelihood of survival [5]. Additionally, a 2013 study found that mortality rates were significantly higher among socially isolated and lonely elders [7]. Loneliness has a profound effect on our healthcare system and has been linked to a higher degree of healthcare utilization. In a Swedish study from 2014, researchers found that lonely elders use more outpatient services than non-lonely elders [8]. In 2015, Gerst et al. found that the large proportion of elders over 60 years old that reported feelings of loneliness had a significantly higher physician visit rate [9].

There is a demonstrated need for intervention in this lonely, elderly population, with significant public health implications. A randomized control trial from 1999 implementing a visitor volunteer program for the elderly showed that strong community involvement increased

the participants' feelings of worth, social integration, and life satisfaction [10]. More recently, a local food delivery project in Tampa showed that weekly food delivery to an at-risk elderly population decreased participants' feelings of loneliness and increased their measured well-being over the course of two months [11]. While both pilot programs had short evaluation periods, they demonstrated the effectiveness of volunteer-based community involvement. Combining a visitor volunteer program with a food delivery service could serve to effectively combat the elderly community's feelings of loneliness and social isolation.

A local food delivery project in Tampa showed that weekly food delivery to an at-risk elderly population decreased participants' feelings of loneliness and increased their measured well-being over the course of two months [12]. Even though it demonstrated the effectiveness of volunteer-based community involvement, the project was constructed as a pretest-posttest, descriptive study using convenience sampling, and feelings of loneliness were evaluated as a secondary objective using a three-item loneliness screener. In our study, we plan to measure the effects of adding a volunteer visitor to the lunch program; that is, to see if eating meals with a medical student can decrease feelings of loneliness when compared with simply receiving meals through Meals on Wheels. Our study is designed as a randomized control trial in which seniors will be randomly assigned to two groups: paired with a medical student for lunch or not paired with a medical student while still receiving meals.

#### 2.0 Methods

#### 2.1 Aims

We intend to recruit USF medical students as volunteers for the program to allow them the opportunity to improve the well being of the elderly in the community and to participate in service learning. Combining a medical student volunteer program with a food delivery service could serve to effectively address the elderly community's feelings of loneliness and social isolation.

#### 2.1.1 Outcome measures

This RCT will evaluate the effect of a volunteer-based meal program on the feelings of loneliness of elders in the community. We will compare pre- and post-study scores using the R-UCLA scale for loneliness, PHQ-9 for depressive symptoms, and GAD-7 for feelings of anxiety.

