# 2.2 Design

#### 2.2.1 Identification and enrollment of participants

We plan to administer an initial three-item loneliness scale to all 926 existing Meals on Wheels of Tampa participants. From that population, we aim to enroll 66 participants into the lunch program. 33 will be assigned to the intervention group and 33 to the control group.

- *Inclusion criteria* 
  - Enrollees are eligible for the study if they are over 60 years of age, speak English, have feelings of loneliness on the three-item scale, able to give written consent, and answer surveys.
- Exclusion criteria
  - o Elders who are unable to give informed consent or complete trial documentation.

We are planning a study of a continuous response variable from matched pairs of study subjects. Prior data indicate that the difference in the response of matched pairs is normally distributed with standard deviation 1. If the true difference in the mean response of matched pairs is 0.5, we will need to study 33 pairs of subjects to be able to reject the null hypothesis that this response

difference is zero with probability (power) 0.8. The Type I error probability associated with this test of this null hypothesis is 0.05.

The three-item loneliness scale will consist of the following questions: First, how often do you feel that you lack companionship? How often do you feel left out? How often do you feel isolated from others? Answers to these three questions will be in the following format: Hardly ever (1), some of the time (2), or often (3). Existing Meals on Wheels volunteers will carry envelopes with them on their meal delivery routes and deliver the envelopes to the elders along with their meals. The envelopes will contain this questionnaire, a brief description of the study, and a return envelope. The questionnaire will contain space for each elder to fill out basic identifying information and then the three questions. A score of 5 or higher will prompt the investigators to invite the elder to enroll in the study. A waiver for written consent explaining the project and why the participant has been selected will accompany the pre-screener three-item loneliness scale.

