#### 2.2.4 Blinding

The following group of people will blinded:

- Study subjects: Study subjects will not be informed of their assignment.
- Outcome assessors and data analysts: Since the outcome data will be collected using a questionnaire, the possibility of interpretation does not exist. Data analysts will not be informed of the subject assignment and the coding for participant will be as group 1 or 2.

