#### 3.0 Discussion

This project will work to reduce elder participants' feelings of loneliness and consequently build long-term relationships. Additionally, we hope the project will encourage the elder participants to be more involved and feel more connected to their community. We also want this to be a positive experience for medical students. Overall, we hope that this project is beneficial for both the elderly and medical student participants insofar as providing companionship and novel experiences for all involved. We hope to create a lasting program and relationship with Meals on Wheels, so that students will continue to have an opportunity to befriend and interact with those in the Tampa's senior community.

We hope that the RCT design will provide enough care matching controls to allow us to publish and present our results directly comparing seniors that received the lunch visitor intervention to seniors that did not. We plan to publish our results, as well as present at a future geriatrics conference.

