#### 4.0 Trial Status

This the third version of the protocol written on April 25, 2018. Initial recruitment of medical students will begin on June 1, 2018 and continue till August 10, 2018 after which the students will undergo orientation (August 13, 2018). Elders will be given the three-question survey to determine eligibility from July 9th till July 13th. Eligible elders who have provided their written consent will be given a pre-trial survey and randomly assigned into the intervention or the control groups (July 30 – August 3). The trial will last from the 20th of August till the 28th of September, after which post-trial surveys will be administered to both groups starting October 8. Trial structure along with dates are illustrated in Figure 1.

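### Section 2.1.1 should name the baseline-adjusted between-arm comparison, and the matched-pairs power figure should be restated for two independent arms

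*Protocol*

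**What the plan says.** **The comparison.** Section 2.1.1 (Outcome measures) says: "We will compare pre- and post-study scores using the R-UCLA scale for loneliness", and the same for PHQ-9 and GAD-7. That sentence names no contrast between arms, no change score and no baseline adjustment. The sentence before it does call the study an RCT of the programme's effect.

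The arm contrast appears elsewhere:

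- Abstract: "Intervention group responses will be compared to responses of participants that did not receive the lunch meeting intervention".
- Section 1.0 (Background): "to see if eating meals with a medical student can decrease feelings of loneliness when compared with simply receiving meals through Meals on Wheels".
- Section 3.0 (Discussion): "directly comparing seniors that received the lunch visitor intervention to seniors that did not".
- Section 2.2.4 (Blinding) presupposes it: "Data analysts will not be informed of the subject assignment and the coding for participant will be as group 1 or 2".

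**The data.** Section 4.0 (Trial Status) provides a baseline for everyone, "Eligible elders who have provided their written consent will be given a pre-trial survey and randomly assigned into the intervention or the control groups", and a follow-up in both arms, "post-trial surveys will be administered to both groups starting October 8".

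**The sizing.** Section 2.2.1 plans 33 participants per group. It derives that number from matched pairs, assuming that "the difference in the response of matched pairs is normally distributed with standard deviation 1", with a mean difference of 0.5, power 0.8 and Type I error 0.05. Section 2.2.3 randomises consenting individuals 1:1 by a block-stratified method. It names no stratification factors and describes no matching of participants.

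**The concern.** The section that defines the outcomes is the natural place to fix the primary comparison. Its wording fits at least three analyses: before versus after within an arm, change scores compared between arms, and post-study scores compared between arms with baseline adjustment. Only the last two use the randomisation. Of those two, baseline adjustment is usually the more precise and needs nothing that is not already collected. With 33 per arm there is little precision to spare.

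The one quantitative statement about the analysis, the power calculation, is built on a paired design that this trial does not have. The stated 80% therefore describes a different study. A reader cannot tell what power the trial has, because the meaning of SD 1 in a two-arm comparison is left open.

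**Working it through.** **Inputs.** From Section 2.2.1: 33 per arm, difference 0.5, SD 1 (of a matched-pair difference), Type I error 0.05. Sidedness is not stated; two-sided is used because it reproduces the plan's figure. The pre/post correlation r and the ratio k = baseline SD / post SD are not in the protocol. They are assumptions, shown as ranges.

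**1. The plan's own figure.** Normal approximation for pairs: ((1.960 + 0.842) × 1 / 0.5)² = 31.4, so 32 pairs. With the noncentral t, 33 pairs give noncentrality 0.5 × √33 = 2.87 on 32 df and power 0.795; 34 pairs give 0.808. The stated 33 is therefore reproduced, as a paired test.

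**2. The same inputs in two independent arms of 33.**

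- SD 1 as the SD of the analysed quantity (a change score, or an unadjusted post score): noncentrality 0.5 / √(2/33) = 2.03 on 64 df, power 0.516.
- SD 1 as the SD of the difference between two unrelated people: score SD = 1/√2 = 0.71, noncentrality 0.5 / (0.71 × √(2/33)) = 2.87 on 64 df, power 0.808 from post scores alone.

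**3. Precision of adjustment relative to change scores.** With equal pre and post SDs of 1, the variance per person is 2(1 − r) for change and 1 − r² for the baseline-adjusted score. Their ratio is (1 + r)/2. Estimating one covariate slope from 66 people costs a factor of about 1 + 1/62 = 1.016. For unequal SDs the large-sample ratio is (1 − r²)/(1 + k² − 2rk), multiplied by the same factor.

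| Assumed r | 0.3 | 0.5 | 0.6 | 0.7 | 0.8 |
|---|---|---|---|---|---|
| (1 + r)/2 | 0.65 | 0.75 | 0.80 | 0.85 | 0.90 |
| with covariate cost, k = 1 | 0.660 | 0.762 | 0.813 | 0.864 | 0.915 |
| with covariate cost, k = 0.8 | 0.797 | 0.907 | 0.956 | 0.997 | 1.016 |
| with covariate cost, k = 1.25 | 0.510 | 0.580 | 0.612 | 0.638 | 0.650 |

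At k = 1 the variance reduction is 34% to 9%, so 33 per arm works like about 33/0.660 = 50 to 33/0.915 = 36 per arm. Simulation of 20,000 trials per r gave 0.661, 0.765, 0.813, 0.871 and 0.914, in agreement with the k = 1 row. At k = 0.8 and r = 0.8 the gain is nil, or a loss of under 2% once the covariate is paid for. Selecting participants on the loneliness screener could narrow the baseline spread, so k below 1 is plausible.

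**4. Where the loss comes from.** The change-score contrast carries (1 − r) times the chance baseline difference between arms. The variance of that term is (1 − r)² per person, and 2(1 − r) − (1 − r²) = (1 − r)². The imbalance term is thus exactly the large-sample efficiency loss in step 3, not something to add to it.

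**5. Power at 33 per arm, difference 0.5, k = 1, covariate cost included.**

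| Meaning of SD 1 | Change scores, r 0.3 to 0.8 | Adjusted, r 0.3 to 0.8 |
|---|---|---|
| SD of change | 52% throughout | 69% to 55% |
| SD of the score | 39% to 89% | 55% to 91% |

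**The case against.** The strongest reply is that the choice between change scores and baseline adjustment usually belongs in the statistical analysis plan, which was not available for this review. The protocol nowhere says that change scores will be compared, and the quoted sentence is as compatible with adjustment as with change. The arm contrast is stated in three other sections. All of this stands, and it is why the first part is an improvement in wording and efficiency rather than an error.

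Four stronger readings are tempting, and the protocol does not support them:

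- *The trial plans a before-and-after analysis that ignores the controls.* The abstract, background, discussion and group coding all point to a comparison between arms.
- *The trial has chosen an inefficient analysis.* No analysis has been chosen in this document.
- *Chance baseline imbalance would bias a change-score result.* Over randomisations that contrast is unbiased; step 4 shows that imbalance is the lost precision seen from another side.
- *Adjustment is always more precise, or restores 80% power.* The gain depends on r and k and can vanish. Power under adjustment still depends on what SD 1 means.

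It can also be said that the matched-pairs problem is a separate matter. It is, and it does not depend on which model is chosen. It is raised here because the power statement must be rewritten for whichever comparison Section 2.1.1 names. An analysis plan can choose a model, but it cannot make a paired calculation describe two independently randomised arms.

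**Conclusion.** The point holds in two limited parts.

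First, Section 2.1.1 leaves the primary comparison loosely worded when the better one costs nothing. The benefit over unadjusted change scores is about 34% to 9% less variance for r of 0.3 to 0.8 with equal SDs, and as little as none at k = 0.8 and r = 0.8. The range rests on assumed r and k, since the protocol gives neither.

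Second, the 80% power in Section 2.2.1 does not rest on the trial's design. For two independent arms of 33 and a difference of 0.5, unadjusted power is about 52% if SD 1 is the SD of the analysed change or of an unadjusted post score. It is about 81% only if SD 1 is the SD of a difference between two unrelated people. A reader might infer that the trial is underpowered and must grow. That does not follow while the meaning of SD 1 is unstated: one reading supports the planned size.

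**What to change.** Reword Section 2.1.1 along these lines: *The primary comparison is the between-arm difference in post-study R-UCLA, estimated from a linear model with arm, baseline R-UCLA and any factors used to stratify the randomisation. PHQ-9 and GAD-7 are analysed in the same way, each with its own baseline. Within-arm change is descriptive only.* If a statistical analysis plan exists, it should say the same.

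In Section 2.2.1, replace the matched-pairs basis with two independent arms of 33. Say whether SD 1 refers to the score, the change or a between-person difference, and restate the resulting power for the named comparison, with the assumed pre/post correlation if adjustment is counted on.

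The cost is protocol wording only: no new data, visits or participants.

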## 2.1.1.1 Primary outcome measure

We will determine the effectiveness of a volunteer-based lunch program on decreasing feelings of loneliness in elderly participants. The full Revised-UCLA (R-UCLA) scale will be administered before and after the six-week trial period electronically using an iPad and Qualtrics software. There are 20 questions on the scale.

## 2.1.1.2 Secondary outcome measures

We will evaluate whether a volunteer-based lunch program decreases feelings of depression in elderly participants using the patient health questionnaire-9 (PHQ-9). It will be administered before and after the six-week trial period electronically using an iPad and Qualtrics software. There are 9 questions on the questionnaire.

We will also assess whether a volunteer-based lunch program decreases anxiety symptoms in elderly participants using the generalized anxiety disorder 7-item scale (GAD-7). It will be administered before and after the six-week trial period electronically using an iPad and Qualtrics software.

# 2.2 Design

#### 2.2.1 Identification and enrollment of participants

We plan to administer an initial three-item loneliness scale to all 926 existing Meals on Wheels of Tampa participants. From that population, we aim to enroll 66 participants into the lunch program. 33 will be assigned to the intervention group and 33 to the control group.

- *Inclusion criteria* 
  - Enrollees are eligible for the study if they are over 60 years of age, speak English, have feelings of loneliness on the three-item scale, able to give written consent, and answer surveys.
- Exclusion criteria
  - o Elders who are unable to give informed consent or complete trial documentation.

We are planning a study of a continuous response variable from matched pairs of study subjects. Prior data indicate that the difference in the response of matched pairs is normally distributed with standard deviation 1. If the true difference in the mean response of matched pairs is 0.5, we will need to study 33 pairs of subjects to be able to reject the null hypothesis that this response

difference is zero with probability (power) 0.8. The Type I error probability associated with this test of this null hypothesis is 0.05.

The three-item loneliness scale will consist of the following questions: First, how often do you feel that you lack companionship? How often do you feel left out? How often do you feel isolated from others? Answers to these three questions will be in the following format: Hardly ever (1), some of the time (2), or often (3). Existing Meals on Wheels volunteers will carry envelopes with them on their meal delivery routes and deliver the envelopes to the elders along with their meals. The envelopes will contain this questionnaire, a brief description of the study, and a return envelope. The questionnaire will contain space for each elder to fill out basic identifying information and then the three questions. A score of 5 or higher will prompt the investigators to invite the elder to enroll in the study. A waiver for written consent explaining the project and why the participant has been selected will accompany the pre-screener three-item loneliness scale.

A designated investigator will contact potential participants who qualify via telephone. We will explain our goals and outline the framework of the study using an existing phone call template. Elders will be asked if they are willing to accept lunch company. If the elder is interested, the investigator will meet the elder at their residence with an iPad containing the study information, a written consent form, and pre-study assessment tools.

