#### 2.2.3 Randomization and allocation

Eligible and consenting participants are randomized to one of the two study groups in a 1:1 allocation ratio. A block-stratified method using the computer will be used for generation of randomization sequence. The block size will be random. The randomization sequence will be implemented centrally with one of the co-investigator ([name]) who is off site will retain the list. Once a participant is identified the primary investigator will call the off-site co-investigator for assignment. Given that the co-investigator is not on site will ensure adequate allocation concealment.

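### The sample size is calculated for matched pairs, but elders are randomised unmatched to two groups of 33, so the stated 80% power is not established for this design

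*Protocol*

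**What the plan says.** The sample-size paragraph is in Protocol section 2.2.1. It opens "We are planning a study of a continuous response variable from matched pairs of study subjects" and continues "Prior data indicate that the difference in the response of matched pairs is normally distributed with standard deviation 1". It then states "If the true difference in the mean response of matched pairs is 0.5, we will need to study 33 pairs of subjects" in order to reject the null hypothesis that this "difference is zero with probability (power) 0.8", with a type I error of 0.05.

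The design is described differently in four places:

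- Section 2.2.1 itself, on enrolment: "33 will be assigned to the intervention group and 33 to the control group".
- Section 2.2.3, on allocation: "Eligible and consenting participants are randomized to one of the two study groups in a 1:1 allocation ratio", using stratified blocks of random size.
- Section 1.0: "seniors will be randomly assigned to two groups: paired with a medical student for lunch or not paired with a medical student".
- The Abstract, on the comparison: "Intervention group responses will be compared to responses of participants that did not receive the lunch meeting intervention".

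The primary outcome is the 20-item R-UCLA score, taken before and after six weeks (section 2.1.1.1). The protocol gives no SD for an individual's score, no correlation within pairs and no pre/post correlation.

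**The concern.** A paired calculation is valid only if each intervention elder is tied to a particular control elder and the analysis uses the within-pair differences. Nothing in the protocol creates such pairs. The only pairing described is between an elder and a medical student, and control elders have no student. The 33 pairs have simply become 33 elders per group.

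This paragraph is the protocol's only justification for 66 participants. Its SD of 1 is the SD of a difference, so the 0.5 cannot be carried over to a two-group comparison without knowing how that SD relates to the spread of individual scores. A reader who takes the text to promise 80% power for half an SD on R-UCLA may read too much into a null result. Keeping the words about matched pairs also invites a paired analysis of groups that contain no pairs.

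**Working it through.** **Inputs (section 2.2.1).** Mean pair difference 0.5; SD of the pair difference 1; 33 pairs; power 0.80; alpha 0.05; 33 elders per group. Sidedness is not stated. Two-sided is used because one-sided 0.05 would need only 27 pairs (power 0.812). Pair and pre/post correlations are assumed below, because the protocol gives none.

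**1. Reproduce the stated figure.** For a paired test, the normal approximation gives n = ((1.960 + 0.842) × 1 / 0.5)² = 31.4, so 32 pairs. With the noncentral t (df = n − 1, noncentrality 0.5 × √n), 33 pairs give 0.5 × √33 = 2.872 and power 0.795; 34 pairs give 0.808. The stated 33 reproduces as a paired calculation.

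**2. Two independent groups of 33.** Noncentral t with df = 2n − 2 = 64 and noncentrality d × √(n/2), where d is the difference in individual SDs.

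- d = 0.5: 0.5 × √16.5 = 2.031, power 0.516.
- 80% power at d = 0.5: 63 per group give 0.795 and 64 give 0.801, so 64 per group.
- Difference detectable with 80% power at 33 per group: d = 0.70.

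**3. Keep the stated SD of 1 for the pair difference.** With pair correlation ρ, the individual SD is 1/√(2(1 − ρ)), so d = 0.5 × √(2(1 − ρ)).

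| Assumed ρ | Individual SD | d | Unpaired power, 33 per group | Per group for 80% |
|---|---|---|---|---|
| 0 | 0.707 | 0.707 | 0.81 | 33 |
| 0.25 | 0.816 | 0.612 | 0.69 | 43 |
| 0.5 | 1.000 | 0.500 | 0.52 | 64 |
| 0.75 | 1.414 | 0.354 | 0.29 | 127 |

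**4. Read the pairs as pre and post scores of one elder.** The stated calculation then covers change within one arm. Comparing mean change between two arms of 33, with SD of change 1 and a between-arm difference of 0.5, again gives noncentrality 2.031 and power 0.516.

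**5. Baseline-adjusted comparison (ANCOVA), individual SD 1.** The residual SD is √(1 − r²) for pre/post correlation r, with df = 63.

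| Assumed r | Residual SD | Power for 0.5 SD | Detectable at 80% |
|---|---|---|---|
| 0.5 | 0.866 | 0.64 | 0.61 SD |
| 0.6 | 0.800 | 0.71 | 0.56 SD |
| 0.7 | 0.714 | 0.80 | 0.50 SD |

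**The case against.** The strongest reply takes the text literally. The SD of 1 belongs to the difference between two subjects. If those subjects are in fact unmatched, their correlation is zero, the individual SD is 0.707, and 33 per group has about 81% power for a difference of 0.5. On that reading the number survives, and quoting 52% alone would be unfair. This stands: the trial cannot be said to have 52% power. The rescue has a price, however. It requires zero correlation in a paragraph about matched subjects, and the effect it powers is 0.71 of an individual SD, which the text does not say. The 81% and 52% figures are also not rivals. They are two points on one power curve for 33 per group, and what is unknown is which effect, in which SD units, was meant.

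A sponsor might also point to the Discussion, which hopes the design will supply matching controls, or to the stratified blocks in section 2.2.3. Neither helps. The first describes no matching procedure, and stratified blocks balance groups without forming elder-to-elder pairs.

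An unseen statistical analysis plan may specify a baseline-adjusted analysis, which could reach 80% for 0.5 SD if the pre/post correlation is about 0.7. That would not correct the protocol paragraph, which would still describe a different design.

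Finally, the arithmetic is correct as far as it goes, and neither type I error nor the validity of the randomised comparison is affected. That is accepted: the fault is a formula that does not fit the design.

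**Conclusion.** The concern holds. The sample size is derived for matched pairs, and the trial compares two unmatched randomised groups, so the 80% power is not established for the comparison to be made. With two-sided alpha 0.05 and no baseline adjustment, 33 per group gives 80% power for about 0.70 of an individual SD and about 52% for 0.5.

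Whether this falls short of the intention depends on what the SD of 1 means. If it is the SD of the difference between unrelated elders, power is about 81%. If the intended effect is 0.5 of an individual SD, or 0.5 SD of change between arms, it is about 52%. The protocol does not settle the matter. Because this is its only basis for 66 participants, the paragraph must be corrected.

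**What to change.** Remove the references to matched pairs from section 2.2.1 and replace the paragraph with a calculation for two independent groups. Possible wording:

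> With 33 participants per group, a two-sided two-sample t-test at the 0.05 level has 80% power to detect a between-group difference of about 0.70 SD in R-UCLA score (about 52% for 0.5 SD).

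State that the SD is that of an individual's score. If a baseline-adjusted analysis is primary, give its detectable difference instead, with the assumed pre/post correlation and its justification: 0.61, 0.56 or 0.50 SD for correlations of 0.5, 0.6 or 0.7. It would also help to express the difference in R-UCLA points and to show it after expected loss to follow-up.

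The cost is protocol wording only; enrolment and procedures stay as they are. If 0.5 was meant in individual SDs, the declared detectable effect becomes less favourable, unless a pre/post correlation of about 0.7 can be supported. If the SD of 1 was that of a difference between unrelated elders, the detectable effect is essentially unchanged (0.70 against 0.71 SD) and is now stated openly.

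### The stated power of 0.8 is for 33 matched pairs with unit-free inputs, but the trial compares two unpaired arms of 33 on the R-UCLA, where power for 0.5 SD may be about 0.52

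*Protocol*

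**What the plan says.** Protocol section 2.2.1 plans the sample size for matched pairs of subjects and a continuous response that it does not name. It says: "Prior data indicate that the difference in the response of matched pairs is normally distributed with standard deviation 1". It continues: "If the true difference in the mean response of matched pairs is 0.5, we will need to study 33 pairs of subjects" to reject the hypothesis that this "difference is zero with probability (power) 0.8". On the error rate it says: "The Type I error probability associated with this test of this null hypothesis is 0.05". No unit, scale or source accompanies the SD of 1 or the difference of 0.5.

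The same section says "we aim to enroll 66 participants into the lunch program", 33 to each group.

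Section 2.1.1.1 makes loneliness on the R-UCLA the primary outcome: "The full Revised-UCLA (R-UCLA) scale will be administered before and after the six-week trial period electronically", and "There are 20 questions on the scale". The protocol gives no R-UCLA scoring range, SD or target difference in points.

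Section 1.0 (last paragraph) and section 2.2.3 describe 1:1 random assignment of individual seniors to two groups. Neither describes matching elders into pairs. The only matching in the protocol is of an elder to a student (Abstract).

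**The concern.** The power paragraph differs from the rest of the protocol in three ways.

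- **Design.** It uses a paired formula, but the trial compares two independent arms.
- **Outcome.** Its inputs are not tied to the R-UCLA. The one local project whose loneliness measure section 1.0 describes was a pretest-posttest study in which "feelings of loneliness were evaluated as a secondary objective using a three-item loneliness screener". That is neither the R-UCLA nor matched pairs of subjects.
- **Losses.** The number enrolled equals the number the formula needs analysed.

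The reader therefore cannot tell what difference in loneliness the trial has 80% power to detect. If power is well below 0.8, a non-significant result could be taken as evidence that student visits do not help, when the trial was too small to show a moderate effect.

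**Working it through.** **Inputs from the protocol (section 2.2.1):** difference 0.5, SD 1, alpha 0.05, power 0.8, 33 pairs, 33 per arm. Sidedness is not stated. Two-sided is used because it reproduces the stated figure; one-sided 0.05 would need only 27 pairs.

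**Assumed, not in the protocol:** loss rates, correlation between baseline and follow-up, SD of the R-UCLA in points.

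**1. The protocol's own figure.** For a paired t-test, the normal approximation gives n = ((1.960 + 0.842) × 1 / 0.5)² = 31.4, so 32 pairs. In the exact calculation the noncentrality is 0.5 × √33 = 2.87 on 32 degrees of freedom, and power is 0.795. With 34 pairs it is 0.808. The stated 33 pairs and power 0.8 therefore reproduce, up to rounding.

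**2. The comparison the trial makes.** For two independent arms of n, the noncentrality is (difference / per-arm SD) × √(n/2) on 2n − 2 degrees of freedom. Taking 0.5 as a multiple of the per-arm SD, with 33 per arm, this is 0.5 × √16.5 = 2.03 on 64 degrees of freedom, and power is 0.516. The difference detectable with 80% power is 0.70 SD. Power of 0.80 for 0.5 SD would need 64 per arm.

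**3. Other readings, 33 per arm.**

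| Reading of 0.5 and SD 1 | Standardised difference used | Power |
|---|---|---|
| Per-arm SD 1, unadjusted | 0.5 | 0.52 |
| Per-arm SD 1, baseline-adjusted, correlation 0.5 | 0.5/√(1 − 0.25) = 0.577 | 0.64 |
| Per-arm SD 1, baseline-adjusted, correlation 0.7 | 0.5/√(1 − 0.49) = 0.700 | 0.80 |
| SD 1 is that of the difference between two unrelated elders, so per-arm SD is 1/√2 = 0.707 | 0.5/0.707 = 0.707 | 0.81 |

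**4. Losses.** With no loss, the paired calculation is already at 0.795; losing one pair gives 0.782. For two arms, assumed losses of about 10% and 20% leave 33 × 0.9 = 29.7, about 30, and 33 × 0.8 = 26.4, about 26 per arm.

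| Per arm | Unadjusted power for 0.5 SD | Difference detectable with 80% power |
|---|---|---|
| 33 | 0.52 | 0.70 SD |
| 30 | 0.48 | 0.74 SD |
| 26 | 0.42 | 0.79 SD |

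**5. Could the inputs be R-UCLA points?** If the score is a sum of 20 items and the item differences are independent with equal variance, a total SD of 1 needs an item SD of 1/√20 = 0.22, and less if the items correlate positively. Most people would have to differ on almost no item. That is implausible for a summed total, but the protocol states no scoring rule that would make it impossible.

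**6. What 0.70 SD means in points.** At assumed R-UCLA SDs of 6, 8, 10 or 12 points, 0.70 SD is 4.2, 5.6, 7.0 or 8.4 points. The protocol gives nothing from which to choose among these.

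**The case against.** The strongest reply is that power depends only on the ratio of the difference to the SD. Read as standardised, 0.5 over 1 gives 0.795 for 33 pairs on any scale, the R-UCLA included. That stands. A reader might infer that the inputs cannot be R-UCLA points and that the stated power is wrong for that reason. The protocol does not support this: missing units leave the figure unexplained, not incorrect, and the most that can be said of the points reading is that it is implausible for a summed total. Likewise, a reader who took 0.5 as literal points and supplied an SD of several points would get very low power, but that combines an implausible reading with SDs found nowhere in the document.

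A second reply is that 0.52 depends on treating SD 1 as a per-arm SD without adjustment. This also stands as a limit on the size of the problem. The R-UCLA is collected at baseline, an adjusted analysis may be specified in an analysis plan not shown here, and two of the four readings above return about 0.80. It does not rescue the paragraph, which specifies neither of those readings and describes pairs that the trial does not form.

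Third, no loss rate is given, so the 10% and 20% are illustrations. It remains true that the enrolment target has no margin.

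**Conclusion.** The concern holds in a limited form. The paired calculation is arithmetically sound but answers a question the trial does not ask. For the between-arm comparison, two-sided at 0.05 with 33 per arm and no loss, power for the stated 0.5 ranges from about 0.52 (standardised on a per-arm SD, unadjusted) to about 0.80 or 0.81 (baseline correlation 0.7, or SD 1 taken as that of the difference between two unrelated elders). Under the first reading, 80% power is available only for about 0.70 SD. Any loss lowers these figures; at the assumed rates the unadjusted power falls to 0.48 or 0.42.

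Attributing SD 1 to prior data is unsupported as written. If the inputs are standardised, the SD is 1 by definition and needs no data. If they are not, a scale and source are needed. This does not show that no such data exist, since the source is simply unnamed.

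**What to change.** Rewrite the sample-size paragraph in section 2.2.1 and leave the sample size unchanged:

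- State whether 0.5 is a standardised effect and of which SD: per-arm score, change, or between-subject difference.
- Cite an R-UCLA source for the SD, or delete the attribution to prior data.
- Replace the matched-pairs power with the power and smallest detectable difference for the between-arm comparison, baseline-adjusted if that is the planned analysis, with the assumed correlation given.
- Give the detectable difference in SD units and in R-UCLA points, for a stated assumed range of SDs.
- Report both at 33 per arm and at the number expected to complete.

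The cost is a revision of protocol wording and, probably, a less favourable stated power. No participants are added.
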